4.3. Prohibitions and Restrictions

Potential subjects must be willing and able to adhere to the following prohibitions and restrictions during the course of the study to be eligible for participation:

[figure not shown]
- Subjects agree to follow the contraceptive requirements as noted in the inclusion criteria.

5. DOSAGE AND ADMINISTRATION

Daratumumab is to be administered as described in Figure 2. Each cycle is of 28 days. The first visit of a cycle should be 4 weeks after the start of the previous cycle. The start of each cycle may occur ± 3 days of the scheduled day in order to accommodate the schedule of the site or subject. The start of each cycle should be scheduled relative to Cycle 1 Day 1 and should not change if within-cycle visits have shifted within the allowed window. In Cycles 1 through 6, daratumumab infusions may be given within ± 1 day of the scheduled day in order to accommodate the schedule of the site or subject.

A schematic of study treatment administration is provided in [Figure 2](#).

Figure 2: Schematic Overview Study Treatment Administration

5.1. Daratumumab preparation

The infusion solution will be prepared on the day of the planned infusion. Detailed instructions for preparation and administration of daratumumab will be supplied in the Site Investigational Product Procedures Manual (SIPPM) or equivalent document.

5.2. Daratumumab Administration

Daratumumab will be administered as an IV infusion. Each subject's dose will be calculated based on the subject's weight at Cycle 1 Day 1 rounded to the nearest kilogram. There is no cap on the absolute dose allowed, as long as the dose does not exceed 16 mg/kg. The dose of daratumumab will remain constant throughout the study, unless the subject's weight changes more than 10% from Cycle 1 Day 1. Subjects will receive preinfusion medications and postinfusion medications as outlined in [Section 5.3](#).

The dilution volumes, initial infusion rates, and increment for the first, second, and subsequent doses are provided in [Table 2](#). The first infusion, with a volume of 1,000 mL, takes approximately 8 hours; the second and subsequent infusions, with volumes of 500 mL, take approximately 4 hours. The maximum infusion rate for all infusions is 200 mL/hour. The sponsor may modify the infusion rates or the preinfusion medications prospectively based upon the information collected to date from this and other studies. Additional details for administration times and rates, as well as preinfusion medications, will be provided in the administration guidelines (study site investigational product and procedures manual).

Table 2: Daratumumab Infusion Rates

	Dilution Volume	Initial Infusion Rate (first hour)	Incremental Increases in Infusion Rate	Maximum Infusion Rate
First infusion	1,000 mL	50 mL/hour	50 mL/hour every hour	200 mL/hour
Second infusion^a	500 mL	50 mL/hour	50 mL/hour every hour	200 mL/hour
Subsequent infusions^b	500 mL	100 mL/hour	50 mL/hour every hour	200 mL/hour

^a Modified rates should only be used if the first infusion of daratumumab was well-tolerated as defined by an absence of > Grade 1 infusion-related reactions during the first 3 hours.

^b Modified rates should only be used if the first 2 infusions of daratumumab were well-tolerated as defined by an absence of > Grade 1 infusion-related reactions during a final infusion rate of ≥ 100 mL/hr.

As noted in the [T&E Schedule](#), vital signs should be monitored extensively on Cycle 1 Day 1 before, during, and after the first infusion of daratumumab. For all other infusions, vital signs should be measured before the start of the infusion and at the end of the infusion. If a subject experiences any significant medical event, then the investigator should assess whether the subject should stay overnight for observation. If the subject has not experienced a significant medical event but is hospitalized overnight only for observation, then the hospitalization should not be reported as an SAE. In instances of daratumumab-related toxicity management, schedule adjustments for daratumumab administration are outlined in [Table 3](#).

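### Footnote a to Table 2 limits second-infusion rates that do not differ from the first, so read literally its tolerability condition has no effect, while the halved volume is unconditional

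*Protocol*

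**What the plan says.** All the relevant statements are in Protocol Section 5.2, Daratumumab Administration.

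- Table 2, first infusion (volume, initial rate, increment, maximum): "1,000 mL 50 mL/hour 50 mL/hour every hour 200 mL/hour".
- Table 2, second infusion, in the same order: "500 mL 50 mL/hour 50 mL/hour every hour 200 mL/hour".
- Table 2, subsequent infusions: "500 mL 100 mL/hour 50 mL/hour every hour 200 mL/hour".
- Footnote a, attached to the label of the second-infusion row: "Modified rates should only be used if the first infusion of daratumumab was well-tolerated". Well tolerated means no IRR above Grade 1 during the first 3 hours.
- Body text on volume: "the second and subsequent infusions, with volumes of 500 mL, take approximately 4 hours". It attaches no tolerability condition.
- Body text on dose: "The dose of daratumumab will remain constant throughout the study, unless the subject's weight changes more than 10% from Cycle 1 Day 1". The milligram dose is therefore normally the same at infusions 1 and 2.

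Further detail on preparation and rates is left to site manuals (Time and Events Schedule footnote h, Sections 5.1 and 5.2, and Section 5.3.3 when an IRR occurs). These manuals are not among the documents.

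**The concern.** Footnote a is the only tolerability condition in the protocol on moving from the first-infusion to the second-infusion set-up. It speaks of rates, but the rates in the two rows are the same. What changes is the volume, which has its own column, is not mentioned in the footnote, and is fixed at 500 mL by the body text for every second infusion. Footnote b, on the subsequent-infusion row, does have a rate difference to govern: an initial 100 mL/hour instead of 50.

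At the same mL/hour, the same dose in half the volume is delivered twice as fast in milligrams. A site that follows the literal text would do this in the subjects the footnote appears meant to protect. A site that reads the footnote as covering the whole row would set up the infusion differently.

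Two things are at stake. The first is the safety of subjects who reacted to infusion 1. Section 5.3.3.3 requires discontinuation if a Grade 3 IRR, or laryngeal edema or bronchospasm of Grade 2 or higher, recurs at a later administration, so the set-up of infusion 2 may also bear on who stays on treatment. The second is the consistency of the IRR data. SAP Section 6.1 summarises treatment-emergent IRRs and SAP Section 2.2 pools all centers, so any difference between sites in second-infusion set-up would be pooled into one summary.

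**Working it through.** **Inputs, all from Protocol Section 5.2.** Dose 16 mg/kg, taken as constant. Volumes 1,000 mL (first) and 500 mL (second). Both start at 50 mL/hour and rise by 50 mL/hour every hour to 200 mL/hour.

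**Step 1: reproduce the stated duration of the second infusion.** 50 + 100 + 150 = 300 mL in 3 hours; the remaining 200 mL at 200 mL/hour takes 1 hour. The total is 4.0 hours, which agrees with the text's approximate 4 hours. The table has therefore been read correctly, and the text's figure assumes 500 mL on this rate schedule.

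**Step 2: drug rate at each step.** mg/kg/hour = (mL/hour) × 16 / volume in mL.

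| Hour | mL/hour (both) | First infusion, 1,000 mL | Second infusion, 500 mL | Ratio |
|---|---|---|---|---|
| 1 | 50 | 0.8 | 1.6 | 2.0 |
| 2 | 100 | 1.6 | 3.2 | 2.0 |
| 3 | 150 | 2.4 | 4.8 | 2.0 |
| 4 | 200 | 3.2 | 6.4 | 2.0 |

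**Step 3: drug delivered in the first 3 hours, the window that footnote a uses.** First infusion: 0.8 + 1.6 + 2.4 = 4.8 mg/kg, or 300/1,000 = 30% of the dose. Second infusion: 1.6 + 3.2 + 4.8 = 9.6 mg/kg, or 300/500 = 60%.

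**Step 4: whole-infusion average.** Without interruption the first infusion takes 3 hours for 300 mL plus 700/200 = 3.5 hours, in total 6.5 hours. Averages: 16/6.5 = 2.46 mg/kg/hour against 16/4 = 4.00, a ratio of 1.63. The doubling is a statement about each scheduled hour, not about the average.

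**Step 5: look for a rule elsewhere.** Sections 5.3.3, 5.3.3.1 and 5.3.3.2 cover interrupting, pausing, restarting, stopping and withdrawal. Section 5.3.3.3 covers discontinuation on recurrence. None says which volume or Table 2 row applies at infusion 2 after a reaction at infusion 1.

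**Step 6: who could be affected.** Only subjects with an IRR above Grade 1 in the first 3 hours who go on to infusion 2. Grade 1 reactors meet the definition of well tolerated. Subjects with a Grade 4 IRR are withdrawn (Section 5.3.3.2), as are some with Grade 2 or 3 reactions (Sections 5.3.3.1 and 5.3.3.2). In Section 1.3.3, 48% of myeloma subjects on 16 mg/kg monotherapy had an IRR, and 95% of those had one at the first infusion: 0.48 × 0.95 = 0.456, about 46%. Grade 3 IRRs occurred in 3%, with none of Grade 4 or 5. The share above Grade 1 within 3 hours is not given.

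**The case against.** The strongest reply is that the footnote hangs on the row label, not on a rate cell, and that the row includes the volume. Table 2 as a whole is titled as a table of infusion rates. A reader may fairly take the entire second-infusion set-up to be conditional, with a subject who did not tolerate infusion 1 staying on the first row; the mg/hour then does not double. This reading is plausible and may be what was meant. It does not remove the problem: it puts the footnote in conflict with the unconditional 500 mL in the body text, and the fallback is still unwritten.

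Second, the working instructions are in manuals that are not available here, and dilution is a preparation matter. They may resolve the point. That stands, and it means that what sites actually do cannot be inferred from the protocol.

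Third, other protections apply at infusion 2: premedication, postinfusion corticosteroid, observation, and the interruption and discontinuation rules. In the earlier monotherapy data only 5% (8/156) had an IRR in more than one infusion. This limits the expected harm. The documents do not say which set-up those reactors received at infusion 2, so it does not show that the condition is unnecessary.

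Three stronger readings are tempting, and the documents do not support them. One is that every subject who reacts to infusion 1 will get double the mg/hour; this fails on the points about the footnote's scope, the manuals and the grades. Another is a count of affected subjects; it would need a share above Grade 1 within 3 hours for which there is no source. The third is that "The first infusion, with a volume of 1,000 mL, takes approximately 8 hours" contradicts the 6.5 hours implied by Table 2. That 6.5 hours is an uninterrupted minimum, and the stated figure is approximate. The observed medians in Section 1.3.3 (7, 4.6 and 3.4 hours) all exceed the corresponding minimums of 6.5, 4.0 and 3.25 hours (the last being 450 mL in 3 hours plus 50/200 hour).

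**Conclusion.** The point holds as an internal inconsistency in Section 5.2. A stated tolerability condition restricts nothing as written, because the rates it names are the same in both rows and the quantity that changes is assigned without condition. On the literal reading, a subject with an IRR above Grade 1 in the first 3 hours who continues may receive twice the scheduled mg/hour at each step. That is 9.6 against 4.8 mg/kg over the first 3 hours, with an average about 1.6 times as high. These figures assume 16 mg/kg, an unchanged dose and no interruption.

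The inconsistency itself is certain from the text. Its practical consequence is not: it depends on how the footnote is read and on the unseen site manual, and the number of subjects affected cannot be derived. The definition of the primary endpoint, ORR by central review, is not touched. Correction is worthwhile because the point concerns subject safety and the comparability of second-infusion IRR data.

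**What to change.** Reconcile footnote a, the first two rows of Table 2 and the volume statement in the Section 5.2 text, and align the site manual with them. Together they should state:

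- whether the tolerability condition governs the dilution volume, the rate, or both;
- which row of Table 2 a subject follows, for volume and for rate, when the condition is not met;
- whether the 500 mL in the body text is subject to the same condition.

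Which set-up applies is for the sponsor to decide; this review takes no view on it. The cost is a wording change in Section 5.2 and a matching check of the site manual. If the sponsor decides that the condition covers volume, some second infusions will take longer.

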5.3. Guidelines for Prevention of Infusion Reactions

5.3.1. Preinfusion Medication

In an effort to prevent infusion related reactions, all subject will receive the following medications 1 to 3 hours prior to each study drug administration (1 hour prior to study drug administration is preferred):

- An antipyretic: Paracetamol (acetaminophen) 650-1,000 mg IV or per oral (PO)
- An antihistamine: diphenhydramine 25-50 mg IV or PO, or equivalent but avoid IV use of promethazine (see [Attachment 3](#) for Family of antihistamine medications that may be used)
- A corticosteroid: Methylprednisolone 100 mg IV for the first 2 infusions, 60 mg IV for all subsequent infusions, administered approximately 1 hour prior to daratumumab infusion. If methylprednisolone is not available, an equivalent intermediate-acting or a long-acting corticosteroid may substitute (refer [Attachment 2](#) for Conversion Table).
- Leukotriene inhibitor (optional) on Cycle 1 Day 1: montelukast 10 mg PO, or equivalent and can be administered up to 24 hours before infusion as per investigator discretion.

If necessary, all PO preinfusion medications may be administered outside of the clinic on the day of the infusion, provided they are taken within 1-3 hours before the infusion. If the preinfusion medication is provided via IV, it should be administered within 1-3 hours prior to daratumumab infusion.

5.3.2. Postinfusion Medication

For the prevention of delayed IRRs, all subjects will receive long- or intermediate-acting corticosteroid PO (20 mg methylprednisolone or equivalent in accordance with local standards) on the 2 days following the first 3 daratumumab infusions (beginning the day after the infusion date). In the absence of infusion-related AEs after the first 3 infusions, postinfusion corticosteroids should be administered per investigator discretion.

For subjects with higher risk of respiratory complications (ie, subjects who have COPD with an FEV1 <80% at screening or developed FEV1 <80% during the study without any medical history or subjects with mild asthma), the following postinfusion medications are recommended:

- Antihistamine (diphenhydramine or equivalent) on the 2 days following all daratumumab infusions (beginning the day after the infusion)
- Leukotriene inhibitor (montelukast or equivalent)

- Short-acting β_2 adrenergic receptor agonist such as salbutamol aerosol
- Control medications for lung disease (eg, inhaled corticosteroids \pm long-acting β_2 adrenergic receptor agonists for subjects with asthma; long-acting bronchodilators such as tiotropium or salmeterol \pm inhaled corticosteroids for subjects with COPD).

In addition, these at-risk subjects may be hospitalized for monitoring for up to 2 nights after a daratumumab administration. If subjects are hospitalized, then their FEV1 should be documented before discharge. If these subjects are not hospitalized, then a follow-up telephone call should be made to monitor their condition within 48 hours after all infusions. If the subject has not experienced a significant medical event but is hospitalized overnight only for observation, then the hospitalization should not be reported as an SAE. Investigators may prescribe bronchodilators, H1-antihistamines, and corticosteroids that are deemed necessary to provide adequate supportive care in the event a bronchospasm occurs after subjects are released from the hospital/clinic. If an at-risk subject is taking postinfusion medications and experiences no major IRRs, then these medications may be stopped after 4 full doses, at the investigator's discretion.

Any postinfusion medication will be administered after the infusion has completed.

5.3.3. Management of Infusion-Related Reactions

Subjects should be carefully observed during daratumumab infusions. Trained study staff at the clinic should be prepared to intervene in case of any IRRs occurring, and resources necessary for resuscitation (eg, agents such as epinephrine and aerosolized bronchodilator, also medical equipment such as oxygen tanks, tracheostomy equipment, and a defibrillator) must be available at the bedside. Attention to staffing should be considered when multiple subjects will be dosed at the same time.

If an IRR develops, then daratumumab administration should be temporarily interrupted. Please see the investigational product preparation instructions (IPPI) for further details. Subjects who experience AEs during daratumumab administration must be treated for their symptoms. Subjects should be treated with acetaminophen, antihistamine, or corticosteroids, as needed. Intravenous saline may be indicated. For bronchospasm, urticaria, or dyspnea, subjects may require antihistamines, oxygen, corticosteroids, or bronchodilators. For hypotension, subjects may require vasopressors. In the event of a life-threatening IRR (which may include pulmonary or cardiac events) or anaphylactic reaction, daratumumab should be discontinued and no additional daratumumab should be administered to the subject.

5.3.3.1. Infusion-Related Events of Grade 1 or Grade 2 (mild to moderate)

If the investigator assesses a Grade 1-2 IRR adverse event to be related to administration of study drug, then the daratumumab administration should be paused. When the subject's condition is stable, daratumumab administration may be restarted at the investigator's discretion.

If the subject experiences a Grade 2 or higher event of laryngeal edema, or a Grade 2 or higher event of bronchospasm that does not respond to systemic therapy and does not resolve within 6 hours from onset, then the subject must be withdrawn from daratumumab treatment.

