5.3.3.2. Infusion-Related Reactions of Grade 3 (severe) or Higher

For IRR adverse events (other than laryngeal edema or bronchospasm) that are Grade 3, the daratumumab administration must be stopped and the subject must be observed carefully until resolution of the adverse event or until the intensity of the event decreases to Grade 1, at which point the daratumumab administration may be restarted at the investigator's discretion. If the intensity of the adverse event returns to Grade 3 after restart of the daratumumab administration, then the subject must be withdrawn from daratumumab treatment.

For IRR adverse events that are Grade 4, the daratumumab administration must be stopped and the subject withdrawn from daratumumab treatment.

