5.3.3.3. Recurrent Infusion-Related Reactions

If a Grade 3 IRR (or Grade 2 or higher event of laryngeal edema, or a Grade 2 or higher event of bronchospasm) recurs during or within 24 hours after a subsequent daratumumab administration, the daratumumab treatment must be discontinued.

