6.1.1. Daratumumab-Related Toxicity Management

Refer to Section 5.3 for details on management of IRRs. The study treatment must be held if any of the following criteria below are met, to allow for recovery from toxicity, regardless of relationship to daratumumab. The criteria for a dose delay are:

1. Grade 4 hematologic toxicity, except for grade 4 lymphopenia
2. Grade 3 thrombocytopenia with bleeding
3. Febrile neutropenia
4. Neutropenia with infection, of any grade
5. Grade 3 or higher non-hematologic toxicities with the following exceptions:
 - a. Grade 3 nausea that responds to antiemetic treatment within 7 days
 - b. Grade 3 vomiting that responds to antiemetic treatment within 7 days
 - c. Grade 3 diarrhea that responds to antidiarrheal treatment within 7 days
 - d. Grade 3 fatigue that was present at baseline or that lasts for <7 days after the last administration of daratumumab
 - e. Grade 3 asthenia that was present at baseline or that lasts for <7 days after the last administration of daratumumab.

Administration of daratumumab may be restarted upon recovery from toxicity to Grade 2 or better or baseline, with the exception that Grade 2 laryngeal edema or Grade 2 bronchospasm must be fully recovered.

If a daratumumab administration does not commence within the prespecified window (Table 3) of the scheduled administration date, then the dose will be considered a missed dose. Administration may resume at the next planned dosing date. A missed dose will not be made up.

Table 3: Daratumumab-Related Toxicity Management

Cycles	Frequency	Dose Held	Dosing Restart*
1 and 2	Weekly (Q1W)	>3 days	next planned weekly dosing date
3 to 6	Biweekly (Q2W)	>7 days	next planned biweekly dosing date
7+	Every 4 weeks (Q4W)	>14 days	next planned every 4 weeks dosing date

*Dosing on Day 1 of a cycle must not be skipped.

Cycles may be delayed up to 4 weeks (Cycle 1 to Cycle 6) or up to 6 weeks (Cycle 7 and beyond). If a dose is delayed on Day 1 of a cycle, then the dates of all the subsequent doses should be adjusted accordingly to maintain the 28-day cycle duration. However, if a within-cycle dose is delayed, then the dates of the subsequent doses should **not** be adjusted.

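### The stopping rule for infusion-related laryngeal edema is internally inconsistent: Protocol 5.3.3.1, read by its punctuation, ends treatment at the first Grade 2 or higher event, while 5.3.3.3 and 6.1.1 presuppose further dosing

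*Protocol*

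**What the plan says.** Four parts of the protocol bear on laryngeal edema and bronchospasm.

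- **5.3.3.1 (headed Grade 1 or Grade 2).** The general rule for a related Grade 1-2 reaction is a pause ("then the daratumumab administration should be paused"), with restart at the investigator's discretion once the subject is stable. A second paragraph singles out the two airway events. Its opening words name both: "If the subject experiences a Grade 2 or higher event of laryngeal edema, or a Grade 2 or higher event of bronchospasm". In full, the second limb is "a Grade 2 or higher event of bronchospasm that does not respond to systemic therapy and does not resolve within 6 hours from onset". The consequence is "then the subject must be withdrawn from daratumumab treatment".
- **5.3.3.2 (headed Grade 3 or higher).** The stop, observe and restart rule carries an exclusion: "For IRR adverse events (other than laryngeal edema or bronchospasm) that are Grade 3, the daratumumab administration must be stopped". For the reactions it covers, restart requires resolution or a fall to Grade 1. Any Grade 4 infusion reaction means withdrawal.
- **5.3.3.3 (recurrence).** "If a Grade 3 IRR (or Grade 2 or higher event of laryngeal edema, or a Grade 2 or higher event of bronchospasm) recurs" during a later administration, or within 24 hours after it, treatment must be discontinued.
- **6.1.1 (toxicity holds).** It first refers management of infusion reactions to Section 5.3. It then allows restart on recovery to Grade 2 or better or baseline, "with the exception that Grade 2 laryngeal edema or Grade 2 bronchospasm must be fully recovered".

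The discontinuation list in 9.2 only points back to Section 5.3. The opening text of 5.3.3 separately requires discontinuation for life-threatening or anaphylactic reactions.

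**The concern.** A stopping rule with a mandatory consequence should give one answer for one event. For a first Grade 2 laryngeal edema that resolves promptly, a site that takes 5.3.3.1 by its punctuation withdraws the subject. A site that takes the condition as covering both events, a reading that fits 5.3.3.3 and 6.1.1, may dose again. Nothing in the protocol tells sites which reading is meant.

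Subject safety and exposure come first. The SAP is also touched, because Section 4.2 summarizes reasons for stopping treatment and Section 6.1 summarizes adverse events leading to discontinuation and infusion-related reactions. Those entries would then depend partly on how each site read the sentence.

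**Working it through.** The plan gives no figure for this rule, so the main check is to set the texts side by side.

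**Step 1. Two readings of 5.3.3.1.** Reading A attaches the response and 6-hour condition to bronchospasm only. The comma before the second limb, and the repetition of the grade threshold in that limb, favor it. Reading B attaches the condition to both events.

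**Step 2. Apply each reading.**

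| Event | Reading | First event, 5.3.3.1 | Can 5.3.3.3 operate? | Can restart under 6.1.1 operate? | Result |
|---|---|---|---|---|---|
| Laryngeal edema, Grade 2 or higher | A | Withdraw always | No, there is no later dose | No, for an infusion reaction | Conflict |
| Laryngeal edema, Grade 2 or higher | B | Withdraw if unresponsive and unresolved at 6 hours | Yes | Yes | Consistent |
| Bronchospasm, Grade 2 or higher | A or B | Withdraw if unresponsive and unresolved at 6 hours | Yes | Yes | Consistent |

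The conflict therefore arises for one event under one reading, and that reading is the one the punctuation supports.

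**Step 3. Does the cross-reference in 6.1.1 settle it?** If 6.1.1 leaves infusion reactions wholly to Section 5.3, its restart clause might concern only events that are not infusion-related. That would remove 6.1.1 from the conflict. It would not reconcile 5.3.3.1 with 5.3.3.3, since both lie inside Section 5.3.

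**Step 4. A first Grade 3 bronchospasm that responds or resolves within 6 hours.** It escapes the withdrawal sentence in 5.3.3.1 and is excluded from the Grade 3 rule in 5.3.3.2. Within 5.3.3 the only specific text is a sentence under a Grade 1-2 heading, and that sentence sets no recovery grade before restart. Section 6.1.1 would require full recovery if it applies, but its deferral to 5.3 leaves that unclear.

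**Step 5. Expected frequency.** Inputs: 1 laryngeal edema among 156 subjects on 16 mg/kg monotherapy, all grades (Protocol 1.3.3, where it is given as 0.6%; 1/156 = 0.64%). The sample size is 32, or 32 + 35 = 67 if the optional expansion is fully enrolled (Protocol 10.2).

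- Expected events: 32 × 1/156 = 0.21; 67 × 1/156 = 0.43.
- Chance of at least one: 1 − (155/156)^32 = 0.19; 1 − (155/156)^67 = 0.35.

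The rule starts at Grade 2 and the rate covers all grades. At that rate, these are upper figures for the events in question.

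**The case against.** The best defense is that the conflict depends on grammar. Sections 5.3.3.3 and 6.1.1 treat the two airway events in parallel, which gives some support to Reading B, and under it everything fits. Even under Reading A, one can say that the laryngeal edema limb of 5.3.3.3 is merely redundant: it never operates, and neither it nor the permissive restart clause in 6.1.1 expressly overrides a mandatory withdrawal. The most severe events are covered elsewhere (5.3.3 and the Grade 4 rule in 5.3.3.2).

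Much of this is fair. But a recurrence rule that can never apply to an event it names shows that the text has not been reconciled, and the protocol does not say that Reading B is meant.

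A reader might also infer more than the documents support:

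- **That bronchospasm is contradictory too.** It is not. Its withdrawal at a first event is conditional, and withdrawal, restart and recurrence then follow in sequence.
- **That 5.3.3.3 withdraws subjects only on recurrence.** It makes recurrence a trigger and does not call it the only one.
- **That bronchospasm frequency measures the problem.** Protocol 1.3.3 gives 4 of 156, which would mean a 56% chance of at least one case in 32 subjects (1 − (152/156)^32). That figure belongs to the event without the contradiction.
- **That nasal-type disease raises the risk of these reactions.** The documents give no figure for this.

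**Conclusion.** The point stands for laryngeal edema. By its punctuation, 5.3.3.1 withdraws the subject at a first Grade 2 or higher event, and this does not fit 5.3.3.3 or, so far as it governs infusion reactions, 6.1.1. A separate and smaller gap concerns which text governs restart after a first Grade 3 bronchospasm that responds or resolves.

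The likely number of affected subjects is small: about 0.2 expected laryngeal edema events and a 19% chance of any in 32 subjects, or 35% in 67. This assumes that the earlier monotherapy rate carries over to this population. That rate rests on a single case, so it is imprecise. The reason to act is that the rule is mandatory and concerns an airway event. The primary analysis gives no reason: sample size, alpha and power are unaffected. No view is offered on which clinical rule is right.

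**What to change.** Reconcile 5.3.3.1, 5.3.3.2, 5.3.3.3 and 6.1.1 for these two events. The amended text should:

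1. state whether the response and 6-hour condition applies to laryngeal edema as well as bronchospasm;
2. state which section governs restart after either event, including a first Grade 3 bronchospasm that responds or resolves, and what recovery is required;
3. place the rule under a heading that matches the grades it covers, and remove or align the sentences that then conflict.

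A single table by event, by grade, and by first occurrence or recurrence would do this. The content of each cell is for the sponsor's safety physicians. The cost is amendment wording and a notice to sites, with no added procedures or subjects.
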